**7.5 Preparation/Handling/Storage/Accountability**

Guidance and information on preparation, handling, storage, accountability, destruction, or return of the investigational product during the study are provided in the IPIM.

**7.6 Treatment Compliance**

Investigational product will be administered in the clinic by a qualified healthcare provider as a subcutaneous injection. Study clinic staff will note the dose and time of dosing on the CRF.

**7.7 Treatment of Overdose**

In high-dose preclinical studies, the noted effects were related to the pharmacological action of romiplostim. Overdose may result in an excessive increase in platelet counts associated with thrombotic/thromboembolic complications. In the event of an investigational product overdose, platelet counts should be monitored frequently and investigational product dose withheld if platelet counts are > 450 x 10^9/L. Reinitiate treatment with investigational product when platelet counts are ≤ 450 x 10^9/L and refer to Section 7.4.1.1 for dosage adjustments.

## 7.8 Prior and Concomitant Treatment

### 7.8.1 Prior Treatment

Prior anti-cancer therapies that were being taken/used from 3 years prior to enrollment through the informed consent will be collected.

For prior therapies being taken for treatment of gastrointestinal, pancreatic, or colorectal cancer, collect therapy name, indication, dose, unit, start date and stop date.

For all other prior therapies, such as radiotherapy, collect therapy name, indication, site (radiotherapy only), dose, unit, frequency route, start date and stop date.

### 7.8.2 Concomitant Treatment

Throughout the study, investigators may prescribe any concomitant medications or treatments deemed necessary to provide adequate supportive care except for those listed in Section 7.1.7.

All concomitant therapies will be collected until completion of **safety follow-up (SFU) 1** and **SFU 2** after which collected concomitant therapies will include the following: platelet related medications: commercial romiplostim, eltrombopag, avatrombopag, lusutrombopag, fostamatinib, and anticoagulants, only.

For platelet transfusions, collect reason, dose, volume, unit, and start date. For all other concomitant therapies, collect therapy name, indication, dose, unit, frequency, start date and stop date.

## 8. Discontinuation Criteria

Subjects have the right to withdraw from investigational product and/or other protocol-required therapies, protocol procedures, or the study as a whole at any time and for any reason without prejudice to their future medical care by the physician or at the institution.

The investigator and/or sponsor can decide to withdraw a subject(s) from investigational product, device, and/or other protocol-required therapies, protocol procedures, or the study as a whole at any time prior to study completion for the reasons listed in Sections 8.1, 8.2.1, and 8.2.2.

### 8.1 Discontinuation of Study Treatment

Subjects (or a legally acceptable representative) can decline to continue receiving investigational product and/or other protocol-required therapies or procedures at any time during the study but continue participation in the study. If this occurs, the

investigator is to discuss with the subject the appropriate processes for discontinuation from investigational product or other protocol-required therapies and must discuss with the subject the possibilities for continuation of the Schedule of Activities (see [Table 2-1](#)) including different options of follow-up (eg, in person, by phone/mail, through family/friends, in correspondence/communication with other treating physicians, from the review of medical records) and collection of data, including endpoints, adverse events, and must document this decision in the subject's medical records. Subjects who have discontinued investigational product and/or other protocol-required therapies or procedures should not be automatically removed from the study. Whenever safe and feasible, it is imperative that subjects remain on-study to ensure safety surveillance and/or collection of outcome data. In particular, the recording of planned chemotherapy administration, which is vital in determining the primary endpoint, can be obtained through medical records if the subject agrees to remain on study despite choosing to discontinue investigational product and other study-related procedures.

Subjects may be eligible for continued treatment with Amgen investigational product(s) and/or other protocol-required therapies by a separate protocol or as provided for by the local country's regulatory mechanism, based on parameters consistent with [12.3](#).

Reasons for removal from protocol-required investigational product(s) or procedural assessments include any of the following:

- Decision by Sponsor
- Lost to follow-up
- Death
- Ineligibility determined
- Protocol deviation
- Non-compliance
- Adverse event
- Subject request
- Requirement for alternative therapy
- Disease progression or relapse per investigator
- Protocol-specified criteria; see Section [7.4](#):
  - Subjects who have a platelet count  $< 100 \times 10^9/L$  for 4 consecutive weeks at the maximum investigational product dose of 10  $\mu g/kg$  should be discontinued from investigational product.
  - Administration of investigational product should be discontinued at any time during the study if neutralizing antibodies to romiplostim or to endogenous TPO are detected.

- Pregnancy

## 8.2 Discontinuation From the Study

Withdrawal of consent for a study means that the subject does not wish to receive further protocol-required therapies or procedures, and the subject does not wish to or is unable to continue further study participation. Subject data up to withdrawal of consent will be included in the analysis of the study, and where permitted, publicly available data can be included after withdrawal of consent. The investigator is to discuss with the subject appropriate procedures for withdrawal from the study, and must document the subject's decision to withdraw in the subject's medical records.

If a subject withdraws from the study, he/she may request destruction of any samples taken and not tested, and the investigator must notify Amgen accordingly (see [Appendix 6](#) for further details).

All subjects who discontinue taking protocol-required therapies, should be encouraged where possible to remain on study to complete the rest of their study visit(s) as would be required by the study protocol. If a subject makes the decision to fully terminate their participation whilst in the trial, the subject should continue to complete the following visits if not already completed:

- the follow-up visit (1 week after the last dose of IP) and
- the first safety follow up visit (SFU 1) (30 days after the last dose of IP)
- the second SFU 2 (30 days after the last dose of on-study cycle of chemotherapy)
- the EOS Visit (if the subject is in LTFU and has completed all the above follow up visits, then the EOS Visit can be completed at the time of terminating their participation from the study)
- If the subject has yet to complete the above follow-up visits, then the EOS Visit should be performed at the same time as the final follow up visit eg, SFU 2.

If the subject does not wish to complete any further visits, then the EOS procedures should be completed (if the subject consents to this) and listed as the subjects last visit on the date the subject decides to terminate early.

### 8.2.1 Reasons for Removal From Washout, Run-in or Invasive Procedures

Not applicable for this study.

### 8.2.2 Reasons for Removal From Study

Reasons for removal of a subject from the study are:

- Decision by sponsor

- Withdrawal of consent from study
- Death
- Lost to follow-up

### **8.3            Lost to Follow-up**

A subject will be considered lost to follow-up if he or she repeatedly fails to return for scheduled visits and is unable to be contacted by the study site.

The following actions must be taken if a subject fails to return to the clinic for a required study visit:

- The site must attempt to contact the subject and reschedule the missed visit as soon as possible and counsel the subject on the importance of maintaining the assigned visit schedule and ascertain whether or not the subject wishes to and/or is able to continue in the study.
- In cases in which the subject is deemed lost to follow-up, the investigator or designee must make every effort to regain contact with the subject (where possible, 3 telephone calls and, if necessary, a certified letter to the subject's last known mailing address or local equivalent methods). These contact attempts are to be documented in the subject's medical record.
- If the subject continues to be unreachable, he/she will be considered to have withdrawn from the study with a primary reason of lost to follow-up.
- For subjects who are lost to follow-up, the investigator can search publicly available records (where permitted) to ascertain survival status. This ensures that the data set(s) produced as an outcome of the study is/are as comprehensive as possible.

## **9.            Study Assessments and Procedures**

Study procedures and their time points are summarized in the Schedule of Activities (see [Table 2-1](#)).

As protocol waivers or exemptions are not allowed if an enrolled subject is subsequently determined to be ineligible for the study, this must be discussed with the sponsor immediately upon occurrence or awareness to determine if the subject is to continue or discontinue study treatment.

Adherence to the study design requirements, including those specified in the Schedule of Activities, is essential and required for study conduct.

### **9.1            General Study Periods**

#### **9.1.1        Screening, Enrollment and/or Randomization**

Informed consent must be obtained before completing any screening procedure or discontinuation of standard therapy for any disallowed therapy. After the subject has

signed the informed consent form, the site will register the subject in the IVRS/IXRS and screen the subject in order to assess eligibility for participation. The screening window is up to 4 weeks.

**At screening, both local and central chemistry and hematology labs are to be performed, however, local lab values may be used for eligibility.**

All screening evaluations must be completed and reviewed to confirm that potential subjects meet all eligibility criteria. The investigator will maintain a screening log to record details of all subjects screened and to confirm eligibility or record reasons for screening failure, as applicable.

If a subject has not met all eligibility criteria at the end of the screening period, the subject will be registered as a screen fail. Screen fail subjects may be rescreened up to 3 times at the discretion of the investigator. Further rescreening requires approval from Amgen Medical Monitors.

Rescreen subjects must first be registered as screen failures in IVRS/IXRS and subsequently registered as rescreens. Once the subject is registered as rescreen, a new 4-week screening window will begin. Subjects will retain the same subject identification number assigned at the original screening. If the rescreening period begins more than 28 days after the original signing of the informed consent form, all screening procedures, including informed consent, must be repeated. If the rescreening **and randomization** occurs within 28 days after the original signing of the informed consent, only those criteria that were originally not met would be required to be repeated.

#### **9.1.2 Treatment Period**

Visits will occur per the Schedule of Activities ([Table 2-1](#)). On-study visits may be completed within  $\pm$  1 day. The date of the first dose of investigational product is defined as day 1, and will occur on the same day as randomization. All subsequent doses and study visits will be scheduled based on the day 1 date and will occur weekly throughout the treatment period. Investigational product is to be administered only after all other study visit procedures have been completed during each visit that it is required. If the subject will be receiving concomitant chemotherapy on a study visit date, investigational product will be administered immediately after the completion of chemotherapy infusion on chemotherapy day 1. If continuous infusion 5-FU over 46-48 hours is part of the chemotherapy regimen the investigational product may be administered prior to beginning or during the continuous infusion 5-FU. Given that subjects will be assessed

for 3 planned cycles of chemotherapy, the oxaliplatin-based chemotherapy cycles are 2-3 weeks in duration, and the investigational product dose adjustment guidelines allow for up to 12 weeks of dosing before a subject is declared a non-responder, the majority of study subjects will receive investigational product for a range of between 7-21 weeks.

#### **9.1.3 End of Treatment**

The treatment period will be long enough to allow for assessment of 3 planned cycles of chemotherapy (see Section 5.1 for details).

The follow-up visit will occur 1 week ( $\pm$  1 day) after the last scheduled dose of investigational product.

#### **9.1.4 End of Treatment Period**

The follow-up visit is scheduled to be 7 days ( $\pm$  1 day) after the last dose of investigational product. End of treatment period (EOTP) is defined as the latest assessment date of that visit. If a subject does not complete a follow-up visit, then EOTP will be 7 days after the last dose of investigational product or the EOS date, whichever is earlier.

#### **9.1.5 Long-term Follow-up**

Subjects will have an in-clinic LTFU Visit 30 (**+5**) days after the last dose of investigational product. (Safety Follow-up 1). Subjects will be contacted 30 days ( $+1$  week) after the last dose of the last on-study cycle of chemotherapy (up to 3 cycles) to collect adverse event information except for females who are in addition required to come to clinic for a highly sensitive urine or serum pregnancy test (Safety Follow-up 2). In addition, after the first LTFU Visit, all subjects will be followed by phone or in clinic every 12 weeks ( $\pm$  2 weeks) **from the last dose of investigational product** until the EOS. During LTFU subjects will be followed for the diagnosis of, or progression to, secondary malignancies (including myeloid malignancies) or myelodysplastic syndromes, as well as vital status and cause(s) of death.

#### **9.1.6 End of Study Visit**

Excluding early termination of the study, the EOS Visit for individual subjects will be defined as up to 2 weeks after the last subject in the trial completes their LTFU Visit 1 year after the last dose of investigational product. EOS Visit can be done by phone.

## **9.2 Description of General Study Assessments and Procedures**

The sections below provide a description of the individual study procedures for required time points.

### **9.2.1 General Assessments**

#### **9.2.1.1 Informed Consent**

All subjects or their legally authorized representative must sign and personally date the IRB/IEC approved informed consent before any study-specific procedures are performed.

#### **9.2.1.2 Demographics**

Demographic data collection including sex, age, race, and ethnicity will be collected in order to study their possible association with subject safety and treatment effectiveness.

#### **9.2.1.3 Medical History**

The investigator or designee will collect a complete medical and surgical history that started 3 years prior to screening through the time of signing of informed consent. Medical history will include information on the subject's concurrent medical conditions. A history of prior and/or concurrent use of alcohol and tobacco will be obtained. Record all findings on the medical history CRF.

#### **9.2.1.4 Physical Examination**

Physical examination will be performed as per standard of care. Physical examination findings should be recorded on the appropriate CRF (eg, medical history, event).

#### **9.2.1.5 Physical Measurements**

Height in centimeters and weight in kilograms should be measured without shoes.

#### **9.2.1.6 Performance Status**

The performance status will be assessed using the ECOG performance status scale.

### **9.2.2 Efficacy Assessments**

#### **9.2.2.1 Platelet Counts**

Platelet counts will be measured at each visit (on a weekly basis) during the treatment period and throughout the 3 on-study cycles to the end of the third study cycle for patients receiving investigational product and non-investigational product. Platelet counts will be assessed locally. If there are multiple platelet values performed on a study visit date, the platelet value from the test performed most immediately prior to the time of the planned investigational product and/or non-investigational product administration will be recorded as the platelet value for that study visit date and will be

used to determine the subject's dose of investigational product and, when applicable, chemotherapy dose modifications which include dose reductions, delays, omissions, and discontinuations. Note: For subjects who discontinue investigational product prior to completing 3 cycles of chemotherapy, platelet counts should be measured through 3 on-study chemotherapy cycles to the end of the third on-study cycle, and the values recorded must be those taken prior to scheduled chemotherapy visits and used to inform decisions relating to chemotherapy dose modification.

#### **9.2.2.2 Bleeding Scale**

Subjects must be assessed for signs and symptoms of bleeding at every weekly visit. These findings must be reported as per CTCAE grading criteria (Miller et al, 1981). Grading is based on physical examination at the time of the visit by the investigator or on patient's history supplemented by available medical reports. Bleeding manifestations reported by the patient but not visible at the time of data collection are graded 1.

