## 4. Objectives, Endpoints and Hypotheses

### 4.1 Objectives and Endpoints

Objectives	Endpoints
Primary	

to evaluate the efficacy of romiplostim for the treatment of chemotherapy-induced thrombocytopenia (CIT) in patients receiving chemotherapy for the treatment of gastrointestinal, pancreatic, or colorectal cancer, measured by the ability to administer on-time, full-dose chemotherapy

	

no thrombocytopenia-induced modification of any myelosuppressive treatment agent in the second and third cycles of the planned on-study chemotherapy regimen. Thrombocytopenia-induced modifications include chemotherapy dose reduction, delay, omission, or chemotherapy treatment discontinuation due to platelet counts below <math>100 \times 10^9/L</math>

Secondary	

to compare the treatment effect of romiplostim with that of placebo on the depth of platelet nadir

	

the depth of the platelet count nadir from the start of the first on-study chemotherapy cycle through the end of the treatment period

to compare the treatment effect of romiplostim with that of placebo on the time to first platelet response

	

the time to first platelet response, defined by platelet count <math>\geq 100 \times 10^9/L</math> in the absence of platelet transfusions during the preceding 7 days

to compare the treatment effect of romiplostim with that of placebo on the incidence of <math>\geq</math> grade 2 bleeding events

	

the duration-adjusted event rate of <math>\geq</math> grade 2 bleeding events, as assessed by Common Terminology Criteria for Adverse Events (CTCAE) version 5.0 grading scale

to compare the treatment effect of romiplostim with that of placebo on overall survival

	

overall survival

to compare the treatment effect of romiplostim with that of placebo on the incidence of platelet transfusions

	

platelet transfusion(s) during the treatment period

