### 9.2.3.1 Adverse Events

#### 9.2.3.1.1 Time Period and Frequency for Collecting and Reporting Safety Event Information

##### 9.2.3.1.1.1 Adverse Events

The adverse event grading scale to be used for this study will be the CTCAE version 5.0 and is described in [Appendix 4](#).

Adverse events possibly related to any study procedures are reported after signing of the ICF. All other adverse events are reported after the first dose of protocol-required therapies (romiplostim/placebo [investigational product], chemotherapy [non-investigational product] up to 3 cycles). The investigator is responsible for ensuring that all adverse events observed by the investigator or reported by the subject that occur after signing of the ICF or from the first dose of protocol-required therapies, as specified above, through the 30 (+5) days after the last dose of protocol-required therapies (last dose of investigational product and last dose of last cycle [up to 3 cycles] of chemotherapy non-investigational product) are reported using the Event CRF. If mandated by country-specific requirements, non-serious adverse events will be collected through the whole duration of the LTFU period until EOS.

Note: For subjects who discontinue investigational product prior to completing 3 cycles of chemotherapy, non-serious adverse events should be collected through 3 on-study chemotherapy cycles.

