### Recording Adverse Events and Serious Adverse Events

#### **Adverse Event and Serious Adverse Event Recording**

- When an adverse event or serious adverse event occurs, it is the responsibility of the investigator to review all documentation (eg, hospital progress notes, laboratory, and diagnostics reports) related to the event.
- The investigator will then record all relevant adverse event/serious adverse event information in the Event case report form (CRF).

- The investigator must assign the following adverse event attributes:
  - Adverse event diagnosis or syndrome(s), if known (if not known, signs or symptoms);
  - Dates of onset and resolution (if resolved);
  - **Did the event start prior to the first dose of investigational product;**
  - **Assessment of seriousness;**
  - Severity (or toxicity defined below);
  - Assessment of relatedness to Amgen investigational product (romiplostim or placebo) or other protocol-required therapies; mandated study activity/procedure;
  - Action taken; and
  - **Outcome of event.**
- If the severity of an adverse event changes from the date of onset to the date of resolution, record as a single event with the worst severity on the Event CRF.
- It is not acceptable for the investigator to send photocopies of the subject's medical records to Amgen in lieu of completion of the Event CRF page.
- If specifically requested, the investigator may need to provide additional follow-up information, such as discharge summaries, medical records, or extracts from the medical records. In this case, all subject identifiers, with the exception of the subject number, will be blinded on the copies of the medical records before submission to Amgen.
- The investigator will attempt to establish a diagnosis of the event based on signs, symptoms, and/or other clinical information. In such cases, the diagnosis (not the individual signs/symptoms) will be documented as the adverse event/serious adverse event.

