Endpoints: Secondary (3) – Duration-adjusted Event Rate of \geq Grade 2 Bleeding Events

The duration-adjusted event rate (**events/100 subject-years**) is defined as the number of grade ≥ 2 bleeding events, divided by the total duration (in 100 subject-years) that subjects have been on study from study day 1 to the earliest of last dose of IP + 30 days or EOS.

Bleeding events will be recorded on the adverse events case report form (CRF) and graded using the CTCAE version 5.0. Bleeding events will be identified using the narrow search of haemorrhages standardized MedDRA query (SMQ), using the MedDRA version 25.1 or later.

Abbreviations:

- b.events = Bleeding Events (Haemorrhages)
- Status = 1 (recurrence of b.event)
- Status = 0 (no b.event)

Censoring Rules:

- Subject with at least one or more than one “grade ≥ 2 b.events”
 - Subject may report multiple b.events, each b.event will be flagged with “Status = 1”.
 - Subject may report multiple b.events, if any b.event end date is missing then also “Status = 1”.
 - The treatment period from last b.event start date to Min(last dose of IP date+30, Study End date) will be considered as no event period, reported as “Status = 0”
- The subjects who do not report any “grade ≥ 2 b.events”
 - These subjects will be included in analysis with “Status = 0”.

Notes:

Status variable will be assigned considering “Haemorrhages” SMQ only, irrespective of number of other adverse event(s) experienced by subject.

- **Status is the censoring variable which will be utilized into the PHREG.**

Endpoints: Secondary (4) –Overall Survival

Overall survival time will be calculated from study day 1 to death. Subjects who have not died will be censored at their last date of contact.

Endpoints: Secondary (5) – Platelet Transfusion

Platelet transfusions during the treatment period is defined as a subject having at least one platelet transfusion after during study period as recorded on the transfusions CRF.

Endpoints: Secondary (6) – Achieving a platelet count $\geq 100 \times 10^9/L$

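### Protocol 9.2.2.2 gives conflicting grading instructions for patient-reported bleeding, and its grade 1 rule, if carried into the CRF, drops resolved bleeds from the grade 2 or higher bleeding endpoint

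*Protocol*

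**What the plan says.** Protocol Section 9.2.2.2 (Bleeding Scale) contains four instructions:

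- Timing: "Subjects must be assessed for signs and symptoms of bleeding at every weekly visit".
- Scale: "These findings must be reported as per CTCAE grading criteria". No version is given, and the citation is a 1981 paper on reporting cancer treatment results.
- Basis for the grade: physical examination at the visit, or the patient's "history supplemented by available medical reports".
- The rule at issue: "Bleeding manifestations reported by the patient but not visible at the time of data collection are graded 1".

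Other sections govern the same grade:

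- Protocol Section 4.1 defines the endpoint as the duration-adjusted rate of grade 2 or higher bleeding, "as assessed by Common Terminology Criteria for Adverse Events (CTCAE) version 5.0 grading scale".
- Protocol Section 9.2.3.1.1.1: "The adverse event grading scale to be used for this study will be the CTCAE version 5.0".
- Protocol Appendix 4, on an adverse event whose severity changes between onset and resolution: "record as a single event with the worst severity on the Event CRF".
- SAP Section 5, Secondary (3): "Bleeding events will be recorded on the adverse events case report form (CRF) and graded using the CTCAE version 5.0".

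None of these other sections makes the grade depend on whether the bleed can be seen at the visit. The SAP neither adopts nor overrides the Section 9.2.2.2 rule, and it plans no sensitivity analysis for it.

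**The concern.** Many bleeds are short. The protocol's own list of symptoms (Section 3.2.1) includes nosebleeds, gum bleeding and excessive bleeding from cuts, any of which may be over by the next weekly visit. A bleed that was grade 2 at its worst and has stopped can be grade 1 under one instruction and grade 2 under another. Neither document says which instruction fixes the CRF grade that the analysis reads.

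The threshold matters because the endpoint counts only grade 2 and above. A bleed entered as grade 1 is not a smaller contribution; it is no event in the Andersen-Gill model. The test also gates others in the fixed sequence: if it fails, overall survival, platelet transfusion and week-4 platelet response are not tested.

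**Working it through.** **1. One bleed under each rule.** Take a bleed that was grade 2 at its worst and is no longer visible at the visit.

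| Rule | Patient report only | Patient report plus medical record |
|---|---|---|
| 9.2.2.2, last sentence, read literally | 1 | 1 |
| 9.2.2.2, sentence before it | 2, arguably, from history | 2 |
| Appendix 4, worst severity | 2 | 2 |
| Endpoint and SAP: CTCAE v5.0 grade on the adverse event CRF, no visibility condition | 2 | 2 |

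The left column is where the rules collide most clearly. In the right column a site can reasonably rely on the history-and-reports sentence.

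**2. Effect on the analysis variable.** SAP Section 5 sets Status = 1 for each grade 2 or higher bleed. Entered as grade 2, the bleed has Status = 1. Entered as grade 1, it contributes only censored follow-up time.

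**3. Place in the sequence (SAP Section 9.1).** Primary, nadir, time to first platelet response, bleeding, overall survival, transfusion, week-4 response. Bleeding is the third secondary endpoint and the fourth of seven tests; three tests lie behind it.

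**4. Size.** The documents give no bleeding rate, effect size, power or share of bleeds not visible at the visit, so there is no planned figure to reproduce. As an illustration on assumed inputs, let E be the number of true grade 2 or higher events and f the share lowered to grade 1. With 2:1 allocation and two-sided 0.05:

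power = Φ( √[E(1 − f) × (2/3) × (1/3)] × |ln HR| − 1.96 )

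For E = 30, HR = 0.5, f = 0: √(30 × 2/9) × 0.693 − 1.96 = −0.17, which gives 43%.

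| E | HR | f = 0 | f = 0.10 | f = 0.25 | f = 0.50 |
|---|---|---|---|---|---|
| 15 | 0.5 | 24% | 22% | 19% | 14% |
| 30 | 0.5 | 43% | 40% | 34% | 24% |
| 60 | 0.5 | 72% | 67% | 59% | 43% |
| 30 | 0.35 | 77% | 73% | 65% | 48% |

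At HR 0.5 the loss runs from about 2 points (15 events, 10% capped) to about 28 points (60 events, 50% capped). The formula treats events as independent, which is optimistic for recurrent bleeds.

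**5. Bias.** The expected rate ratio is multiplied by (1 − f in the romiplostim arm)/(1 − f in the placebo arm).

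- Equal shares: factor 1, no bias.
- 50% romiplostim, 25% placebo: 0.50/0.75 = 0.67, so a true ratio of 0.5 would appear as 0.33.
- 25% romiplostim, 50% placebo: 0.75/0.50 = 1.5, so a true ratio of 0.5 would appear as 0.75.

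**The case against.** The best defence reads the two sentences of Section 9.2.2.2 together: documented bleeds are graded from history and records, and only uncorroborated self-report is held at grade 1. Limiting the grade of unverified reports is a defensible measurement choice. Bleeds that lead to hospitalization are serious adverse events and would normally leave records. The SAP reads the CTCAE v5.0 grade from the adverse event CRF, and nothing says the Section 9.2.2.2 rule overrides that field. The trial is double-blind, so sites should not apply the rule differently by arm.

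Much of this stands, and it rules out several stronger conclusions that a reader might draw:

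- *Every bleed not seen at the visit is capped.* The rule concerns patient-reported bleeding, and a documented bleed can keep its grade under the preceding sentence.
- *Events are certainly lost.* Loss depends on sites applying the rule to the CRF grade.
- *The rule contradicts the wording of CTCAE v5.0.* The CTCAE criteria are not reproduced in the documents. What can be shown is that the endpoint and adverse event sections invoke that scale with no visibility condition.
- *Bleeding is understated throughout the safety tables.* Haemorrhage as an event of interest is summarized with no grade threshold stated, so a bleed entered as grade 1 still counts there. Only grade-dependent summaries could change.
- *Readers are sent to a 1981 scale.* The same paragraph names CTCAE and other sections fix version 5.0; the citation is clerical.

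The defence does not remove the conflict. The joint reading has to be supplied by the reader, since the last sentence has no exception and says nothing about corroboration. Even on that reading, a grade 2 bleed known only from the patient is grade 1 under Section 9.2.2.2, against the worst-severity rule. Blinding guards against sites grading differently by arm, but it does not ensure that the share of bleeds over by the visit is equal if treatment changes how long bleeds last. The documents offer no data on that.

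**Conclusion.** The point holds as a conflict between grading instructions that should be resolved before unblinding. It is not a demonstrated loss of events. If sites apply the last sentence of Section 9.2.2.2 to the CRF grade, patient-reported bleeds of grade 2 or higher that resolved between visits, mainly those without records, fall out of the third-ranked secondary endpoint. If some sites apply it and others do not, the same bleed is graded differently across the trial.

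The size cannot be determined from the documents. The 2 to 28 point power loss rests wholly on assumed event counts, capped shares, a hazard ratio of 0.5 and independent events. A reader might infer that the treatment comparison is biased. That follows only if the capped share differs between arms; equal capping lowers event count and power and leaves the expected rate ratio unchanged. The primary endpoint is not affected.

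**What to change.** Before unblinding:

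1. In Protocol Section 9.2.2.2, delete the last sentence, or state that it does not apply to the adverse event CRF grade used for the endpoint. Add that all bleeding since the last visit, visible or not, is graded by CTCAE v5.0 at its worst severity from examination, history and available records.
2. In SAP Section 5, Secondary (3), add one line naming that CRF grade as the one that governs the endpoint.
3. As an editorial matter, replace the 1981 citation with CTCAE v5.0.

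The cost is a short protocol clarification, a CRF completion note to sites and one SAP line, with no new visits or procedures. The downside is slightly more reliance on patient history. If bleeds have already been entered as grade 1 under the old sentence, the clarification alone will not correct them; a blinded query of those entries would be needed.
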